19.4 Criteria for Suspending/Terminating a Study Site

Boston Scientific reserves the right to stop the inclusion of subjects at a study site at any time after the study initiation visit if no subjects have been enrolled for a period beyond 6 months after site initiation, or if the site has multiple or severe protocol violations/noncompliance without justification and/or fails to follow remedial actions.

The IRB/EC and regulatory authorities, as applicable, will be notified.

20. Study Registration and Results

20.1. Study Registration

To comply with applicable laws and regulations, the study will be registered on a publicly accessible database.

20.2. Clinical Investigation Report

Study results will be made available in accordance with the legal requirements and the recognized ethical principles, in accordance with the Boston Scientific Policy. A Clinical Investigation Report will be made available to all investigators, IRB/EC and regulatory authorities, as applicable in accordance with the Boston Scientific Policy and local requirements. As applicable an abbreviated Clinical Investigation Report will be made available on a publicly accessible database.

22.1. Abbreviations

Abbreviations are shown in Table22.1-1.

Table 22.1-1: Abbreviations

| Abbreviation/Acronym | Term |
|-----------------------------|--|
| AE | Adverse event |
| AUASI | The American Urological Association Symptom Index |
| BPH | Benign prostatic hyperplasia |
| CRF | case report form |
| DUS | Doppler ultrasound |
| eCRF | Electronical case report form |
| FDA | Food and drug administration |
| GCP | Good clinical practice |
| ICH | International Conference on Harmonization |
| IIEF | The International Index of Erectile Function |
| IPSS | International Prostate Symptom Score |
| IRB | Institutional Review Board |
| LCI | Lower confidence interval |
| LUTS | lower urinary tract symptoms |
| MSHQ-EjD | Male Sexual Health Questionnaire Short Form- Ejaculation dysfunction |
| MRI | Magnetic Resonance Imaging |
| PVR | Post Void Residual Urine Volume |
| Qmax | Peak Flow Rate |
| QoL | quality of life |
| SADE | serious adverse device effect |
| SAE | serious adverse event |
| TURP | transurethral resection of the prostate |
| UADE | unanticipated adverse device effect |
| USADE | unanticipated serious adverse device effect |

## Revision History

Document Revision Number	Template Number and Version	Section	Change	Reason for Change
Version-AA	90702621 Rev/Ver AE	Initial document	NA	NA

## 1 PROTOCOL SUMMARY

- **Study title:**

A real world study to evaluate the feasibility, preliminary safety and performance of Rezūm system in BPH treatment in China.

- **Study Objective(s):**

This RWS study is to evaluate the feasibility, preliminary safety and performance of Rezūm system in BPH treatment in China, to generate local real world data from a Chinese BPH population.

- **Study Design:**

This is a retrospective, single arm, RWS study, which will be performed in investigation site, Boao Yiling Life Care Center.

- **Planned Number of Subjects:**

Up to 30 subjects who were diagnosed as BPH and treated with Rezūm system will be collected to get 22 treated subjects with valid data.

- **Planned Number of Centers:**

One (1) investigation site, Boao Yiling Life Care Center

- **Indication(s) for Use:**

The Rezūm System is intended to relieve symptoms, obstructions, and reduce prostate tissue associated with BPH. It is indicated for men  $\geq 50$  years of age with a prostate volume  $\geq 30\text{cm}^3$  and  $\leq 80\text{cm}^3$ . The Rezūm System is also indicated for treatment of prostate with hyperplasia of the central zone and/or a median lobe.

- **(Commercial) Device/System applied**

Rezūm Generator (Model #G2200-0032)

Rezūm Delivery Device Kit (Model # M006D2201-0032)

- **Method of Assigning Patients to Treatment:**

Not applicable, this is a single arm study.

- **Study Duration:**

This is a retrospective study, and it will take about 3 months to complete data collection.

- **Follow-up Schedule:**

Not applicable, this is a retrospective study with no prospective follow up visit.

- **Key Inclusion Criteria:**

- The subjects will provide written informed consent and agree to data collection

- The subjects who were diagnosed as BPH and treated by Rezūm procedure in Hainan medical pilot zone will be enrolled in this study.

- **Key Exclusion Criteria:**

This is a retrospective study without any formal exclusion criteria.

## 2 INTRODUCTION

Benign prostatic hyperplasia (BPH) with associated lower urinary tract symptoms (LUTS) is a common medical condition in the aging male. Progressive prostate enlargement causes bladder outflow obstruction and lower urinary tract symptoms, which have a significant impact on patients' quality of life. For many men, medications are the most common way to control mild to moderate symptoms of BPH to reduce its major symptoms. However, BPH medications have several systemic side effects, are costly if used for long periods of time, and some subjects have difficulty with complying with medications, particularly in the older population. For severe BPH symptoms, transurethral resection of the prostate (TURP), laser vaporization, or thermal ablation are common treatments of choice.

Transurethral resection of the prostate (TURP), which is considered the gold standard intervention, have a high complication rate, such as TRUS, retrograde ejaculation, erectile dysfunction, urethral stricture; and its surgical retreatment rate was 1–2% per year. Furthermore, it requires the use of general or spinal anaesthesia, which may cause more risks for elderly.

The Rezūm System is a minimally invasive thermal ablation treatment that may mitigate the symptoms of BPH. The Rezūm System treatment is rapid, preserves the urethra, and subjects may potentially have relief from the symptoms of BPH as soon as 1 week after treatment. The Rezūm System has got CE mark and FDA approval in 2013 and 2015 respectively, and a series of clinical studies have been conducted worldwide.

In view of the aggravation of the aging process in China and the high incidence rate of male patients over 50 years old, there is a considerable socioeconomic burden to patients and society as it represents the most commonly presenting urological complaint.

This retrospective study will collect the data of treated subjects in the hospitals in BOAO medical pilot zone, to evaluate its safety and performance in Chinese patients, which will provide real world evidence for extensive use in China.

Please refer Protocol Table 9.1-1 Data collection schedule

**Table 9.1-1: The data collection schedule**

Procedure/Assessment	Baseline/pre-procedure	Index Procedure	Post procedure/Prehospital Discharge	follow-up post-procedure #
Informed consent				X&
Demographics	X			
Medical history	X			
Physical examination (height, weight, etc)	X			X
Prostate volume (MRI, DUS)*	X			X
Uroflowmetry(Qmax, Urinary volume )	X			X
PVR	X			X
IPSS	X			X
QoL	X			X
IIEF	X			X
MSHQ-EjD	X			X
Procedure information		X		
Length of catheterization			X	
Surgical retreatment				X
Medication(s) used(LUTS /BPH)	X		X	X
Device Defect (if available)		X		
Adverse events assessment		X	X	X

Note: # All information of subjects available before the defined end of study will be collected in this retrospectively study, data missing will be allowed.

\*Prostate volume -data form MRI and DUS are collected, MRI data will be preferred to used for statistic, DUS data will be used ONLY MRI data unavailable.

&Only written informed consent form is provided after initiation , data will be collected.

### **3 ENDPOINT ANALYSIS**

Primary Efficacy Endpoint: IPSS change at 3-6M post Rezūm procedure.

Primary Safety Endpoint: Device Related Serious Complications at 3-6M post Rezūm procedure.

Composite device related serious complications for this endpoint are defined as:

1. Device perforation of the rectum or GI tract
2. Device related formation of fistula between the rectum and urethra
3. De novo severe urinary retention lasting more than 21 consecutive days post treatment.

#### **3.1 Primary Effectiveness Endpoint**

Primary Efficacy Endpoint is IPSS change at 3-6M post Rezūm procedure.

International prostate symptom score (IPSS) is a questionnaire used to indicate the severity of LUTS symptoms, there are 7 questions relating to different symptoms subjects be experiencing and one question relating to overall quality of life.

IPSS scores will be collected at baseline and post procedure. If several IPSS scores are collected between 90 and 182 days, the last IPSS score for 3-6 months post procedure will be used to assess the primary efficacy endpoint.

Reduction in IPSS score from Baseline = IPSS score at baseline - IPSS score at 3-6M post procedure.

The improvement of IPSS score of 30% will be calculated for 3-6 months post procedure against baseline.

##### **3.1.1 Hypotheses**

$$H_0: \Delta \leq 5.5$$

$$H_1: \Delta > 5.5$$

Where  $\Delta$  = reduction in IPSS score at 3-6 month compared to baseline

The mean reduction in IPSS score at 3-6 month from baseline will be calculated with its 90% confidence interval. If the lower bound of the one-sided 95% CI is greater than 5.5 then the null hypothesis will be rejected, and the primary endpoint will be met.

##### **3.1.2 Sample Size**

In Rezūm Pivotal II study, IPSS score represents a  $11.2 \pm 7.6$ -point reduction at 3M post Rezūm procedure in treatment arm, while  $4.3 \pm 6.9$ -point reduction in sham control. In Pivotal trial, IPSS score in treatment group decreased 25% (5.375) compared to sham control group is recognized as meaningful. For this retrospective RWS study, a performance goal (PG) of 5.5 was deemed as clinically meaningful, and the expected score reduction is assumed to be 10 at 3-6M post Rezūm procedure.

The sample size is calculated according to below formula:

$$n = \frac{(Z_\alpha + Z_\beta)^2 * \sigma^2}{\delta^2}$$

n is sample size,  $\delta = 4.5$  (since 5.5 is the performance goal and 10 is expected IPSS change),  $\sigma = 7.6$ ,  $\alpha=0.05$ ,  $\beta=0.20$  (power=80%). Considering the small sample size needs to be iterative distribution, 22 subjects will provide more than 85% power. As this is retrospective study, there are chances of missing data in the study. A sample size up to 30 are expected to yield 22 treated subjects with available data at 3-6 months post procedure.

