The pivotal study of Rezūm System demonstrated its efficacy and safety. 197 males subjects were enrolled in pivotal study, with a prostate size $> 30 \text{ cm}^3$ but $< 80 \text{ cm}^3$ and IPSS > 13 . All eligible subjects were randomized in a 2:1 ratio to receive either the Rezūm vapor ablation treatment, or a control sham procedure. The primary endpoint, the change in IPSS at 3 months post-procedure were 11.2, 4.3 respectively in the Treatment Arm and the Control Arm. The treatment arm's IPSS was 22 at baseline, which improved at 2 weeks after procedure, and the improvement of IPSS were more than 50% at 3, 6, 12 months post- procedure, Qmax at 3 months post-procedure was improved by 6.2ml/s, and remained consistently durable at 12 months post- procedure; There was no de novo ED, with just mild, moderate AE occurred^[5]; At 2 years post procedure, convective radiofrequency thermal therapy improved urinary symptoms significantly over controls at 3 months procedure (86.9% (53/61) subjects in the

Control Arm had qualified and elected to cross over to receive the Rezūm treatment following their 3-month postprocedure visit.), and provided a sustained 51% reduction from baseline; This produced a 5- and 8-point or greater score decrease in 84% and 74% of subjects , respectively [6]; There were a more than 50% improvement in the IPSS, quality of life, Qmax, BPH impact index at 3 years post procedure, which were maintained during 3 years after procedure, without late AE, surgical retreatment rate was 4.4% at 3, 4,5 years after water vapor thermal therapy^[7,8,9]. As a a minimally invasive medical device, Rezūm System provides effective early onset, as well as enduring relief of LUTS associated with BPH, with an acceptable side effect profile, and can be performed in an outpatient treatment setting with short procedure time.

4.2. *Study Rationale*

Benign prostatic hyperplasia (BPH) is a disease of aging, whose morbidity increases with age. Progressive prostate enlargement causes bladder outflow obstruction and lower urinary tract symptoms, which have a significant impact on patients' quality of life.In view of the aggravation of the aging process in China and the high incidence rate of male patients over 50 years old , there is a considerable socioeconomic burden to patients and society as it represents the most commonly presenting urological complaint.

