In Rezūm Pivotal II study, IPSS score represents a 11.2 ± 7.6 point reduction at 3M post Rezūm procedure in treatment arm, while 4.3 ± 6.9 point reduction in sham control. In Pivotal trial, IPSS score in treatment group decreased 25% (5.375) compared to sham control group is recognized as meaningful.

As this is a retrospective RWS study, the inclusion/exclusion criteria is not strict, we set up performance goal for score change as 5.5, the expected score change is 10 at 3-6M post Rezūm procedure. A performance goal (PG) testing for the primary endpoint is planned. The decision rule is to calculate the Lower Confidence Interval (LCI) of score change and compare it to the PG, meet PG if LCI is greater than PG.

10.1.2. *Sample size*

The sample size is calculated according to below formula:

$$n = \frac{(Z_\alpha + Z_\beta)^2 \sigma^2}{\delta^2}$$

n is sample size, we designed 5.5 as performance value, 10 is expected IPSS change, $\alpha=0.05$, $\beta=0.20$ (power=80%) Considering the small sample size needs to be iterative distribution, 22 subjects will provide more than 85% power. As this is retrospective study, there are chances of missing data in the study. So the final sample size will be up to 30, to satisfy 22 treated subjects.

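### Does the 5.5-point performance goal lack support because its derivation is not written out and it lies inside the pivotal sham arm's confidence interval?

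*SAP*

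**What the plan says.** Protocol 10.1.1 (repeated in the synopsis) and SAP 3.1.2 start from the same pivotal results: a mean reduction of 11.2 (SD 7.6) on treatment and "4.3 ± 6.9 point reduction in sham control". Both then give the same benchmark: "IPSS score in treatment group decreased 25% (5.375) compared to sham control group is recognized as meaningful".

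They part at the next sentence. The Protocol says that because "the inclusion/exclusion criteria is not strict, we set up performance goal for score change as 5.5". The SAP says "a performance goal (PG) of 5.5 was deemed as clinically meaningful". Both assume a true reduction of 10.

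SAP 3.1.1 states the test. The parameter is the mean reduction from baseline to 3-6 months, the null hypothesis is that it is 5.5 or less, and success means that the one-sided 95% lower bound exceeds 5.5. SAP 3.1 also mentions a relative measure: "The improvement of IPSS score of 30% will be calculated for 3-6 months post procedure against baseline".

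**The concern.** Four things make the goal look poorly founded.

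1. Neither document says what the 25% is taken of or why 5.375 became 5.5.
2. The two documents attach different reasons to the same threshold, and only the SAP calls it clinically meaningful.
3. The benchmark is phrased as a comparison with sham, but the study tests a before-after change with no control. If the goal was built on the sham mean, it treats 4.3 as exact, although that mean comes from a modest arm.
4. A 30% improvement, the SAP's only other mark, would be 6.6 points at the pivotal baseline (the Protocol's Background states that the treatment arm's "IPSS was 22 at baseline"). The goal of 5.5 is below that.

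Protocol 6.1 says the data are meant to support approval in China. In a single-arm study the origin of the goal decides what a pass can be said to show. If 5.5 could not be told apart from a sham response, a pass would carry little weight.

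**Working it through.** **Inputs.** Goal 5.5, expected change 10, SD 7.6, one-sided alpha 0.05, n = 22 (SAP 3.1.1 and 3.1.2). Sham mean 4.3, SD 6.9 (Protocol 10.1.1). Control arm of 61, from the crossover figure "86.9% (53/61) subjects in the" Control Arm in Protocol 4.1. That 61 were analysed at 3 months is an assumption. I also used 53 (those who crossed over) and 66 (one third of the 197 enrolled).

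**The plan's own figure.** The normal formula gives n = (1.645 + 0.842)² × 7.6² / 4.5² = 17.6, so 18. Iterating with the t distribution gives 20 for 80% power and 22 for 85%. The noncentral t power at n = 22 is 85.1%, so the SAP's claim of more than 85% holds.

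**Where 5.375 and 5.5 could come from.** Three routes fit:

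- 1.25 × 4.3 = 5.375 (sham mean plus 25%)
- 0.25 × 21.5 = 5.375 (25% of a baseline of 21.5)
- 0.25 × 22 = 5.5 (25% of the pivotal treatment-arm baseline)

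The text does not choose between them. Whichever was meant, 5.5 is at or above the stated benchmark: 5.5 − 5.375 = 0.125 points stricter.

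**Sham interval.** SE = 6.9/√61 = 0.883. The 95% CI is 4.3 ± 2.000 × 0.883 = 2.53 to 6.07. With n = 53 it is 2.40 to 6.20, and with n = 66 it is 2.60 to 6.00. All contain 5.5, which is (5.5 − 4.3)/0.883 = 1.36 SE above the sham mean.

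**What a pass requires.** The goal is compared with the lower confidence bound, not with the observed mean. The study SE is 7.6/√22 = 1.620, and t(0.95, 21) = 1.721. The smallest passing mean is 5.5 + 1.721 × 1.620 = 8.29.

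**What beating sham requires.** Allow for both sampling errors: combined SE = √(1.620² + 0.883²) = 1.846, with about 34 Welch degrees of freedom.

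| Criterion | Observed mean needed |
|---|---|
| Exclude 4.3, one-sided 95% | 4.3 + 1.691 × 1.846 = 7.42 |
| Exclude 4.3, two-sided 95% | 4.3 + 2.032 × 1.846 = 8.05 |
| Pass the SAP test | 8.29 |

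The two-sided figure is 8.11 with 53 sham subjects and 8.02 with 66. Both are still below 8.29.

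**Chance of passing, n = 22, SD 7.6.** True mean 4.3: 0.9%. True mean 5.5: 5.0%. True mean 6.07 (the sham upper limit): 9.6%. True mean 10: 85.1%.

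**The 30% mark.** 0.30 × 22 = 6.6, and 5.5/0.30 = 18.3, so the goal falls short of 30% only if the mean baseline exceeds 18.3. This study sets no minimum IPSS, whereas the pivotal trial required more than 13, so a baseline of 22 cannot be assumed here. The SAP attaches no hypothesis or success rule to the 30% figure.

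**The case for a change.** The strongest case for a change is that a performance goal is the whole comparator in a single-arm study, and the first question put to a sponsor is where it came from. Here the two documents give different answers. The candidate derivations mean different things, since sham plus a quarter is not the same claim as a quarter of baseline, and only the sponsor knows which was intended. Calling 5.5 clinically meaningful could let a pass be reported as proof of clinical benefit. An agreed paragraph written before the data are seen would cost almost nothing. There is also a stronger claim that a pass does not secure: showing 25% more than sham, with the sham arm's error counted, needs an observed mean of about 8.67 and has about 79% power at a true mean of 10.

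Part of this stands. The step to 5.5 is not recorded, the linking clauses differ, and no source is cited for 5.5 as a change from baseline.

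The rest does not. The goal is not unsupported, because the benchmark sentence comes immediately before it in both documents. Loose entry criteria and clinical relevance are compatible reasons, and the figures behind them are identical. The sham interval bears on the goal's origin only if 4.3 was its starting point, which the text leaves open, and it does not show whether 5.5 points matters to a patient. The 8.67 figure answers a question the plan does not ask. SAP 3.1.1 already limits a pass to a mean reduction from baseline above 5.5, and both documents state that the study is single-arm. A further line giving the observed mean minus 4.3 would be an unadjusted comparison across populations and time windows (3 months against 3-6 months). It would invite the sham-relative reading that the objection warns against.

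**Conclusion.** No change to the plan is needed. This is a gap in the recorded rationale, which a reader can largely fill from the adjacent sentence: a 25% benchmark of 5.375, moved up by 0.125 to 5.5.

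The overlap with the sham interval is real, but it does not weaken the test. A pass at the planned size needs about 8.29, which is above the 7.42 (one-sided) or 8.05 (two-sided) that would exclude the sham mean. A true response equal to the sham mean passes 0.9% of the time. The 30% figure is descriptive and does not compete with the goal.

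These results assume 22 evaluable subjects, an SD near 7.6, and between 53 and 66 sham subjects behind the mean of 4.3. Comparing with the sham mean also assumes that the pivotal sham response would carry over to this population, which the documents cannot establish. A fuller derivation would make the documents easier to defend but would not alter the hypothesis, the decision rule, the sample size or any result.

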### 3.1.3 Statistical Methods

Descriptive statistics will be used to summarize the study endpoints. Continuous variables will be tabulated with mean, median, standard deviation, minimum, maximum, and the corresponding 95% confidence interval of the mean. Categorical variables will be tabulated with frequencies, percentages along with the 95% confidence intervals.

### 3.2 Primary Safety Endpoint

Primary Safety Endpoint: Device Related Serious Complications at 3-6M post Rezūm procedure.

Composite device related serious complications for this endpoint are defined as:

1. Device perforation of the rectum or GI tract
2. Device related formation of fistula between the rectum and urethra
3. De novo severe urinary retention lasting more than 21 consecutive days post treatment.

AEs will be collected and relationship to device will be assessed by investigators, it will be assessed whether meet the pre-specific device related serious complications. All serious complications in up to 6 months (i.e. 182 days) post procedure will be used for primary safety endpoint.

Frequencies and percentages will be provided for AE summary.

## **4 GENERAL STATISTICAL METHODS**

### **4.1 Analysis Sets**

The primary effectiveness and safety endpoints will be analyzed on an efficacy analysis set and on safety analysis set respectively. Baseline characteristics and other variables descriptive statistics will be presented for safety analysis set.

#### **4.1.1 Efficacy Analysis Set**

The efficacy analysis set includes subjects with IPSS scores at baseline and at 3-6 months post-procedure.

#### **4.1.2 Safety Analysis Set**

The safety analysis set includes all enrolled subjects who has been treated with Rezūm system in hospitals in Hainan BOAO medical pilot zone.

### **4.2 Control of Systematic Error/Bias**

All subjects treated with Rezūm system in Hainan BOAO medical pilot zone will be enrolled to reduce select bias during given time. The data will be collected completely and accurately.

### **4.3 Number of Subjects per Investigative Site**

Not Applicable as this a single center study.

## 5 ADDITIONAL DATA ANALYSES

### 5.1 Other Endpoints/Measurements

Following are the categorical endpoints:

1. Anesthesia method
2. Surgical retreatment post Rezūm procedure (if available)
3. Medication retreatment post Rezūm procedure (if available)
4. All SAEs

Following are the Continuous endpoints:

1. Rezūm operation time
2. Qmax and Post Void Residual Urine Volume (PVR )
3. Length of Catheterization
4. Quality of Life (if available)
5. Ejective function (MSHQ-EjD and IIEF (if available))

All the above measurements data will be presented in respective exhibits.

Length of catherization = Days from insertion to the removal day

